Vaccines: All vaccines in the study are US FDA licensed.

7- valent Conjugate pneumococcal vaccine (licensed in Feb 2000) is manufactured as a lyophilized preparation requiring reconstitution with saline aluminum phosphate diluent before use. Each 0.5 ml dose of reconstituted vaccine contains 2µg saccharide per serotype 4, 9V, 14, 18C, 19 F and 23F, and 4 µg of serotype 6B (20 µg total saccharide); approximately 20µg of CRM 197 protein; and 0.5 mg of aluminum phosphate. This is a licensed product (Pnevenar®)of Wyeth-Ayerst.

23 valent pneumococcal polysaccharide vaccine contains 25 µg of each polysaccharide type dissolved in isotonic saline solution containing 0.25% phenol as a preservative. It is a mixture of highly purified capsular polysaccharides from 23 most prevalent or invasive pneumococcal types of streptococcus pneumoniae. This is a product (PNEUMOVAX 23) of Wyeth-Ayerst.

The **meningococcal vaccine** contains purified capsular polysaccharides of groups A,C,Y AND W-135 50 mcg of polysaccharide of each serotype. It is a product (Menomune ®) of Connought, used world-wide.

Specimens

See Appendix 1 for the schedule of collection of specific specimens, which will be collected at the follow up observation visits at birth, 6, 10, 14, 18-20 weeks.

Blood (5 ml) will be collected from mothers before and one month after immunization, and at the time of delivery. Infant cord specimens will be obtained at the time at delivery and infant (2ml) sera will be collected at 6, 14, and 18 weeks..

Breast milk will be collected at delivery and at 1, 6 and 18 weeks after delivery

Specimen processing Blood specimens will be centrifuged to separate serum, which will be aliquoted and frozen at -20 C at ICDDR, B until antibody assays are carried out. Breast milk specimens will also be centrifuged and the supernatant aliquoted and frozen at -20 C at ICDDR, B until antibody assays is carried out. All specimens will be labeled with the subject number and a specimen number, and their position in storage boxes will be recorded in the specimen database.

Microbiological processing of nasopharyngeal specimens for colonization study. Nasopharyngeal cultures for pneumococci will be obtained from the infants at birth and at each visit at 6, 10, 14, 18 weeks.

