The primary outcome measures are the infant serum IgG antibody titers to specific capsular pneumococcal polysaccharide, and to the protein carrier moiety of the pneumococcal conjugate vaccine. These data will be generated on coded specimens by the laboratory and reported as microgram per ml for each subject. The comparisons of interest are of the antibody concentrations at birth, which represents passively acquired maternal antibody; and the antibody concentrations after 3 doses of immunization at 18 weeks of age, which represent the active filial antibody response.

Sample size estimate

In order to estimate the sample size required to answer the primary research questions posed in the objectives of this proposal, we used standard sample size formulae and pneumococcal antibody geometric mean and standard deviation data from our studies of the 5 valent Praxis glycoprotein conjugate pneumococcal vaccine given to US infants at 2, 4 and 6 months of age (table 2 below).

Table 1 ANTIBODY MEAN AND SD DATA^{a)}

serotype	N	IgG GMT	mean log	std. dev. of logs	
19F	43	3.6 μg/ml	0.55882	0.605756	
6B	45	2.3 μg/ml	0.36080	0.767809	

^{a)}values are for sera collected at 7 months of age, after 3 doses given at 2, 4 and 6 months of age to US infants

Table 2 utilizes the data in table 1 to show the number of subjects per group which are required to detect the specified differences between the antibody GMTs of groups 1 and 2. Since one goal of the project is to determine if a study group 2 has a lower antibody titer than group 1, a one-sided test of significance is appropriate, however, a 2-sided test allows full examination of the relationships.. A sample size of 63 in each group will allow us to detect a difference of 50% in the final geometric mean titers.

Table 2 SAMPLE SIZE ESTIMATES

group GMT (μg/ml)		Dif	Difference			Number each in group a)		
_ A	B	%	Fold		1 sided	2 sided		
1.8	3.6	-50%	0.5		50	63		
2.5	3.6	-30%	0.7		185	235		
2.7	3.6	-25%	0.75		285	362		
2.9	3.6	-20%	0.80		445	565		

 $^{^{}a)}$ assuming alpha = 0.05, beta = 0.20, power = 80%.

We had 79% rate of completion in our previous study in Dhaka. If 30% of enrolled subjects do not complete the study, $(63 \div 0.7 =)$ 90 subjects will need to be enrolled in each group, for a project total of 180 mother-infant pairs. (Appendix 3)

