Antibody assay validity and variability: Because antibody titers are the principal outcomes of this studies, we have instituted procedures to ensure validity and to reduce the variability of antibody assays. The ELISA for pneumococcal antibody has been standardized using the CDC/WHO standard assay procedures and FDA reference serum by [name] at Johns Hopkins University. Interassay variability is now assessed by running a local control serum (89-1C) on each plate to measure day to day variations. During a recent study of pneumococcal immunization of adults with and without HIV infection the co-efficients of variation for serotypes 6B, 14, 18C, 19F, and 23F were 30%, 12%, 11%, 12%, 16%, respectively. These values were typical for variation as reported by other centers, including the observation that type 6B has greater variability than the remaining serotypes. The laboratory will receive the serum coded and thus they will remain blinded to the code assignments.

Data analysis (see appendix 2)

Sera with undetectable antibody will be assigned half the lower limit of detection for the purposes of calculating means. Because the distributions of antibody titers and of the increases in titer (post-immunization antibody level divided by pre-immunization antibody level) are likely to be positively skewed, the values will be log-transformed to approximate a normal distribution for statistical analyses. The antilogarithms of the means of the log-transformed values will be reported as geometric mean titers (GMT) or as geometric mean increases. Continuous variables will be compared between groups by two-sided T-test or Mann-Whitney U test within groups by the paired T-test, and associations of continuous variables will be assessed by Pearson's correlation coefficient or the Spearman rank correlation test. The Chi Square or Fisher's exact test will be used to compare proportions between groups.

The gestational age of the infants will be estimated by two methods. The mothers will be asked the date of the first day of their last menstrual period, from which we will calculate the duration of the gestation period. In addition, each child will be examined within 48 hours of birth using the method of Ballard to assess the neuromuscular and physical maturity of the infant (25). The Ballard technique assigns a score for neuromuscular and physical maturation and allows an estimation of gestational age.

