In order to determine the success of the randomization procedure, the following variables of the mothers and infants will be compared to determine if the means or proportions are significantly different between the groups: maternal age, height, education, and parity, household size, gestational age at immunization, gestational age at delivery, immunization-birth delivery, birth weight, percent of infants with birth weight less than 2.5 kg, and less than 37 weeks gestation. The geometric mean pneumococcal antibody titers before immunization and at the time of delivery will be compared between mothers in the study groups, by ANOVA. Similarly, the infants' antibody titers to pneumococcal polysaccharide, diphtheria toxoid and tetanus toxoid will be compared between the three study groups in cord, 6 week and 18 week specimens by ANOVA test. The groups will be compared with respect to key characteristics to assess randomization. Proportions with adverse events and proportions seroconverting will be compared using chi-square tests.

We will compare the final infant pneumococcal antibody GMT between study group 1 and 2 to assess the effect of passive antibody on the filial antibody response to three doses of glycoprotein conjugate pneumococcal vaccine.

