Appendix 3 Two-Sample T-Test Power Analysis

Numeric Results for Two-Sample T-Test

Null Hypothesis: Mean1=Mean2. Alternative Hypothesis: Mean1>Mean2 The standard deviations were assumed to be known and equal.

		Α	llocation	•					
Power	N1	N2	Ratio	Alpha	Beta	Mean1	Mean2	S1	S2
0.80286	63	63	1.00	0.02500	0.19714	0.559	0.258	0.601	0.601
0.80514	50	50	1.00	0.05000	0.19486	0.559	0.258	0.601	0.601

Two-Sample T-Test Power Analysis

Numeric Results for Two-Sample T-Test

Null Hypothesis: Mean1=Mean2. Alternative Hypothesis: Mean1>Mean2 The standard deviations were assumed to be known and equal.

			Allocation						
Power	N1	N2	Ratio	Alpha	Beta	Mean1	Mean2	S1	S2
0.80000	40	40	1.00	0.02500	0.20000	0.559	0.182	0.601	0.601
0.80000	50	50	1.00	0.02500	0.20000	0.559	0.222	0.601	0.601
0.80000	60	60	1.00	0.02500	0.20000	0.559	0.251	0.601	0.601
0.80000	70	70	1.00	0.02500	0.20000	0.559	0.274	0.601	0.601
0.80000	80	80	1.00	0.02500	0.20000	0.559	0.293	0.601	0.601
0.80000	90	90	1.00	0.02500	0.20000	0.559	0.308	0.601	0.601
0.80000	100	100	1.00	0.02500	0.20000	0.559	0.321	0.601	0.601
0.80000	40	40	1.00	0.05000	0.20000	0.559	0.225	0.601	0.601
0.80000	50	50	1.00	0.05000	0.20000	0.559	0.260	0.601	0.601
0.80000	60	60	1.00	0.05000	0.20000	0.559	0.286	0.601	0.601
0.80000	70	70	1.00	0.05000	0.20000	0.559	0.306	0.601	0.601
0.80000	80	80	1.00	0.05000	0.20000	0.559	0.323	0.601	0.601
0.80000	90	90	1.00	0.05000	0.20000	0.559	0.336	0.601	0.601
0.80000	100	100	1.00	0.05000	0.20000	0.559	0.347	0.601	0.601

M2 vs N1 by Alpha with M1=0.559 S1=0.601 S2=0.601 Power=0.80 N2=N1 1-Sided T Tes

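### The between-arm comparisons of infant pneumococcal titers use no covariate, although the mother's pre-vaccination titer is available and could add modest precision at almost no cost

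*Protocol*

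**What the plan says.** **Arm comparison.** The Data analysis section plans: "We will compare the final infant pneumococcal antibody GMT between study group 1 and 2 to assess the effect of passive antibody". The general rule there is "Continuous variables will be compared between groups by two-sided T-test or Mann-Whitney U test", on log-transformed titers. The same section compares infant titers at cord, 6 weeks and 18 weeks by ANOVA. None of these sentences names a covariate. Appendix 3 sizes the trial with a two-sample t-test.

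**Baseline sample.** Under Specimens, blood "will be collected from mothers before and one month after immunization" and again at delivery; Appendix 1 shows the pre-vaccination draw in both groups. The laboratory section has each mother-infant pair's sera assayed on one plate for the same pneumococcal serotypes. The one explicit use of the pre-vaccination titer is a between-group ANOVA of mothers, in the paragraph on whether randomization succeeded.

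**Regression.** Data analysis also plans a multivariable regression of final infant titers on maternal titers to pneumococcal polysaccharide, diphtheria and tetanus, birth weight, immunization interval and demographic variables. Appendix 2 lists regression beside the t-test and chi-square for primary objective 1a.

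**The concern.** The pre-vaccination titer precedes the intervention and measures the same antigen as the outcome. The protocol gives its own reasons to expect it to be prognostic. It treats antibody at birth and 6 weeks as passively acquired from the mother, and it asks whether higher cord antibody depresses the 18-week response. In control mothers, who receive no pneumococcal vaccine, existing antibody is the natural source of what reaches the infant. A correlation of either sign reduces the residual variance.

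Adjusting for such a covariate leaves the randomized comparison unbiased, narrows the interval for the GMT ratio and corrects for chance imbalance between arms in maternal immunity. There is little spare power: the design aims at 80% for a halving of the GMT and has no margin above that.

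**Working it through.** **1. Inputs.** Two-sided alpha 0.05 and 80% power (sample size section; Appendix 3 runs it as one-sided 0.025). 63 evaluable infants per group for a halving of the GMT (3.6 to 1.8 µg/ml). SD of log10 titer 0.601 in Appendix 3; Table 1 gives 0.605756 for 19F and 0.767809 for 6B.

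**2. The plan's own figure.** Appendix 3 states: "The standard deviations were assumed to be known and equal". With known SD, n per group = 2 × (1.960 + 0.842)² × 0.601² / 0.301² = 62.6, so 63. Power at 63 is Φ(0.301 / (0.601 × √(2/63)) − 1.960) = Φ(2.811 − 1.960) = 80.3%, against 0.80286 stated. After 30% loss, 63 / 0.7 = 90 per group. The stated figures reproduce.

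**3. Unadjusted power with the Table 1 SDs.** I used the non-central t distribution with 124 degrees of freedom and a difference of log10(2) = 0.301.
- 19F: SE = 0.605756 × √(2/63) = 0.1079; non-centrality 0.301 / 0.1079 = 2.79; power 79.0%.
- 6B: SE = 0.767809 × √(2/63) = 0.1368; non-centrality 2.20; power 58.8%.

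**4. Power with adjustment.** Residual SD = SD × √(1 − r²), where r is the within-arm correlation of the mother's log pre-vaccination titer with the infant's log titer. One degree of freedom goes to the covariate (123 left). The documents do not give r, so the values below are assumptions.

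| r (assumed) | √(1 − r²) | 19F power | 6B power |
|---|---|---|---|
| 0 | 1.000 | 79.0% | 58.8% |
| 0.2 | 0.980 | 80.6% | 60.6% |
| 0.3 | 0.954 | 82.7% | 62.9% |
| 0.5 | 0.866 | 89.2% | 71.3% |

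On the log scale the interval narrows by about 2%, 5% and 13% at r of 0.2, 0.3 and 0.5. At r = 0 the lost degree of freedom does not change power at one decimal.

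**5. Does the planned regression already do this?** Its maternal titer could be the pre-vaccination, one-month or delivery sample; the text does not say. Study arm is not among its listed terms. Birth weight, which is listed, arises after randomization. Its outcome is the final titer only, so cord and 6-week titers are not covered. If arm were added while the maternal titer was the one-month or delivery value, the model would condition on the route by which maternal vaccination acts and would remove part of the effect under test.

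**The case against.** **The unadjusted comparison is valid and matches the sample-size method.** This stands. A reader might infer that the comparison is biased or wrong; under randomization it is neither.

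**The baseline is not shown to serve only as a balance check, nor is a t-test the only method.** A reader might infer both. The documents do not support either. Mann-Whitney and ANOVA are also named, a regression on maternal titers is planned, and Appendix 2 lists regression for objective 1a. Because the maternal sample in that regression is unspecified, use of the pre-vaccination value is neither stated nor excluded.

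**Covariates are commonly left to an analysis plan, which is not shown.** This stands in part. A later plan could add the adjustment without contradicting the protocol. But the protocol does name its between-arm methods, and those are unadjusted.

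**The gain may be small where it was calculated.** This stands. The Table 1 SDs are for sera taken after three conjugate doses. At 18 weeks, inhibition by maternal antibody (negative) and residual passive antibody (positive) would pull r in opposite directions, so it could be near zero. If the relation lies mainly in the control arm, a common-slope model gains less than the control-arm correlation suggests. Larger gains are more plausible at cord and 6 weeks, where no power target is stated.

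**The 6B shortfall is a separate sample-size issue.** This stands: even r = 0.5 leaves 6B at 71%.

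**Same-antigen baselines are not documented for every outcome.** This stands. The protocol does not expressly plan pre-vaccination maternal diphtheria or tetanus titers.

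**Conclusion.** The point holds as a modest, low-cost improvement in precision for the pneumococcal serotypes. The stated arm comparisons are unadjusted, a baseline on the same antigens is collected, and the planned regression does not supply a baseline-adjusted estimate of the arm effect. At 63 per group and a 2-fold difference, the gain is about 2 to 4 points of power at r of 0.2 to 0.3 for either serotype. At r = 0.5 it is about 10 points for 19F and 12 to 13 for 6B. It is nil at r = 0, with almost no penalty. These figures rest on the Table 1 SDs from US infants, on a common within-arm correlation and on assumed values of r. If r at 18 weeks is small, the remaining benefit is protection against chance imbalance in maternal titer.

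**What to change.** In Data analysis, state that:
- infant log pneumococcal titers at cord, 6 weeks and 18 weeks are compared between arms by linear regression on arm plus the mother's log pre-vaccination titer to the same serotype;
- the adjusted GMT ratio is reported with its 95% CI, and the unadjusted test is kept as a sensitivity analysis;
- this comparison is not adjusted for one-month, delivery or cord titers or for birth weight, all of which arise after randomization;
- the multivariable regression names the maternal sample it uses and is kept separate from the arm comparison.

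Extend the adjustment to diphtheria or tetanus titers only if pre-vaccination maternal sera are assayed for them.

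The cost is a few sentences and one degree of freedom. For the pneumococcal serotypes no new specimens or assays are needed, since the pre-vaccination maternal titers are already planned. The sample size need not change.

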Our methodology is a prospective randomized controlled trial to evaluate the effect of maternal immunization with pneumococcal vaccine on the filial antibody response to pneumococcal conjugate vaccine given at 6, 10 and 14 weeks of age. The primary outcome is the antibody titer to selected serotypes of pneumococcal vaccine and to tetanus toxoid. We will specifically compare the association between the levels of antibodies at birth and 6 weeks of age (passive maternal antibodies) with the level at 18-20 weeks of age (filial active antibody response) and at 9 months of age of the infant. As a secondary objective, we will determine the ability of infants in Dhaka to respond to new pneumococcal conjugate vaccine when given in the W.H.O. schedule without the

maternal dose. We will also assess the effect of the infants' serum IgG antibody and maternal IgA antibody in breast milk on colonization of the infants with pneumococci.

If we can show that the strategy of maternal + infant pneumococcal immunization to have a better immune response, then this strategy could be considered an appropriate immunization strategy for the regions to prevent early infant pneumococcal disease. Pneumococcal vaccines are licensed and readily available, and delivery systems to immunize pregnant women and infants are functioning in many developing countries. This strategy is operationally feasible and could have a substantial effect on early infant mortality.

KEY PERSONNEL (List names of all investigators including PI and their respective specialties)

Name	Professional Discipline/ Specialty	Role in the Project
ICDDR,B		
1. [name]	Epidemiology	Principal - Investigator
2. [name] [name]	Epidemiology	Co-investigator
3. [name]	Epidemiology	Co-investigator
3. [name]	Microbiology	Co-investigator
4.To be identified	Immunology	Co-investigator
Johns Hopkins		
1. [name]	Epidemiology	Co- principal - Investigator
2. [name]	Immunology .	Co-investigator
3.[name]	Immunology	Co-investigator
	67	2 2 22.18 01101

DESCRIPTION OF THE RESEARCH PROJECT

Hypothesis to be tested:

To determine the immunogenicity and safety of conjugate pneumococcal vaccine in infants of mothers who have been immunized with pneumococcal polysaccharide vaccine.

Specific Aims:

The specific objectives of the revised project are:

Primary Objectives

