The USFDA licensed 23-valent pneumococcal polysaccharide vaccine covers about 90% of circulating serotypes in Bangladesh (9). It produces high levels of antibody responses in adults (12). A recent study in Bangladesh showed that maternal immunization with the 23-valent polysaccharide pneumococcal vaccine, was safe and immunogenic and protective levels of antibodies (>0.15µg/mL) were observed in the infants' blood up to 22 weeks of age (13). Maternally transferred antibodies play an important role in infant protection, but the antibodies are short lived and may not fully cover the period of high risk. Maternal immunization does not produce impaired responses either with maternal anti-tetanus toxoid (TT) (a protein antigen) or with other polysaccharides as *H. influenzae* B (Hib) in infants (14). This may also induce the effect of priming in the newborn.

Vaccine efficacy depends on the prevalence of the serotypes in the vaccine, the age at which the children become immuno-competent to the predominant serotype, and the naturally acquired immunological response of the children to the important serotypes at the time of immunization (15). In developing countries, the serotypes that cause invasive disease are more likely to be ones that evoke a good immune to immunization in young children (16). Polysaccharide vaccines co-valently linked to a carrier protein are immunogenic in young infants from an early age(15). Clinical trials of the 2,5,7 & 9- valent glycoprotein conjugate pneumococcal vaccine have been conducted in young children both in developing and in developed countries and found to be safe and immunogenic when given along with routine immunization

(17-23). The serotypes in the 7 –valent CRM $_{197}$ product would cover \sim 60% of circulating serotypes here (24).

The proposal is to conduct a prospective randomized, blinded, controlled comparative trial of safety and immunogenicity of 2 US FDA licensed pneumococcal vaccines. Women will be immunized around 32 weeks gestation and infants at birth. To-date no studies have examined the immunogenicity and safety of the conjugate pneumococcal vaccine with maternal immunization.. Globally early infant deaths remain a significant problem, which cannot be addressed with current EPI strategies, even with new vaccines. This project builds on results of a previous study and will build capacity for vaccine evaluation in Bangladesh.

RESEARCH DESIGN AND METHODS:

Study Design:

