A randomized double-blind controlled immunogenicity trial will be conducted in Dhaka in collaboration with private and public facilities providing maternity health care services. In this study mothers will be randomized to receive either the pneumococcal (study) or the meningococcal (control) vaccine All infants will receive the glycoprotein conjugate pneumococcal vaccine.

Setting and Population:

This trial will be carried out in Dhaka, in collaboration with three private and public facilities providing maternity health care services. Pregnant women belonging to the middle-class come to these clinics for ante-natal care and delivery. Healthy pregnant women in the third trimester and their infants will be enrolled after signing informed consent forms. The study population will be pregnant women residing in Dhaka, Bangladesh. Our obstetrical co-investigators have helped us conduct our earlier studies with 180 women. They will again inform their registered patients of the purpose and of the trial, and refer them to our project staff assigned to that clinic. Project staff will provide a detailed explanation of the purpose, procedure, risk and benefits of the trial, answer any questions and then obtain signed informed consent of participation. Assignment to study groups will be instituted as soon as the mother gives concurrence to enroll into the study.

Selection criteria:

Inclusion criteria:

- 1. Women in third trimester of pregnancy with normal medical and obstetric history and physical examination and aged >15 and <40.
- 2. Women who plan to deliver in Dhaka and who plan to remain in Dhaka for the next 12 months.

Exclusion criteria:

- 1. Women with systemic disease as diabetes, hypertension, etc.
- 2. Women with known history of previous complicated pregnancy.
- 3. Women with previous history of preterm delivery and repeated abortions.
- 4. Women with previous history of birth with congenital anomalies.
- 5. Women with hypersensitivity reactions to vaccination.
- 6. Women with receipt of pneumococcal or meningococcal vaccine in last 3 years.

Study Procedure:

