The interview data will be recorded into the data forms by the field team at the time of interviewing the subjects. The completed data forms will be reviewed by the data manager who will determine that the forms are complete without blanks and obvious errors. On a weekly basis the forms will be double- entered into an EpiInfo database, once by one person, and again by another. At each entry range and logical checks will be performed. The two entered files then will be compared; inconsistencies will be resolved in consultation with the research coordinator and the PI. If necessary a specific query will go to the field worker who will contact the subject and resolve the inconsistency. Weekly frequency tables of variables will be reviewed by the PI to discover aberrant data. Quarterly summary tables will be shared with co-PI.

The laboratory data will be also doubled-entered into the data system. Summary tables of frequencies and ranges of antibody data will be reviewed to identify possibly anomalous values. Values, which appear anomalous or out of expected range will be referred to the serology laboratory for review. We will periodically resubmit a random selection of samples for independent assessment of assay variation. In addition, the laboratory has routine procedures for quality control which include periodic documentation of variance of the assay on standard sera.

Threats to validity

Lack of compliance with the intervention is unlikely to be a problem, because all interventions are an injection administered by study staff. Co-intervention in the form of receipt of study vaccines from other sources is also unlikely, since neither pneumococcal nor meningococcal vaccine are readily available in Dhaka. In order to determine the possibility of administration of routine BCG, DPT, OPV or other vaccine in study infants, we will question mothers at each visit if injections or immunization have been given to the child by non-study personnel. The provision of free care and routine immunizations to the infants makes co-intervention an unlikely possibility. Bias due to confounding factors and selection bias will be reduced by the randomization procedures.

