The effect of specific maternal antibody on the filial immune response to pneumococcal conjugate vaccine will be assessed by calculating the correlation coefficient of infant antibody titers at 18 weeks (one month after the third dose of vaccine) with the specific antibody titer in the cord specimen (predictor variable). A negative correlation between the two would imply that higher antibody titers in the cord specimen inhibit the filial production of antibodies after active immunization. To determine if maternal antibody to the carrier protein (diphtheria toxoid) influences the filial antibody response to the glycoprotein conjugate vaccine or to diphtheria vaccine, the correlation of infant pneumococcal polysaccharide and diphtheria toxin antibody titers at 18 weeks with infant cord titers for both antigens will be examined. A negative correlation between cord diphtheria antitoxin antibody levels and final pneumococcal polysaccharide antibody would suggest inhibition related to maternal protein carrier antibodies. Similar analyses of correlation with pneumococcal polysaccharide antibodies will be done using tetanus toxoid antibodies as a control, since both mothers and infants receive tetanus vaccine. A multivariable regression technique will be used to assess the joint and separate effects of maternal antibody titers to pneumococcal polysaccharide, diphtheria and tetanus antigens, birth weight, immunization interval and other demographic variables on the final infant antibody titers to pneumococcal polysaccharide, tetanus and diphtheria toxoids. The natural decay of the antibody will be calculated based on rate of natural decay per week.

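### A negative cord-to-18-week titer correlation is read as inhibition, although cord titer is not randomised and study group is not among the named regression terms

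*Protocol*

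**What the plan says.** The Study Design section fixes what is randomised: "mothers will be randomized to receive either the pneumococcal (study) or the meningococcal (control) vaccine". All infants receive the conjugate vaccine.

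The Data analysis section then approaches the effect of maternal antibody in three ways.

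- **Group comparison.** "We will compare the final infant pneumococcal antibody GMT between study group 1 and 2 to assess the effect of passive antibody" on the infant's response. Appendix 2 puts the t-test under Primary 1a.
- **Correlation.** "The effect of specific maternal antibody on the filial immune response to pneumococcal conjugate vaccine will be assessed by calculating the correlation coefficient" of the 18-week titer with the cord titer. The reading is given in advance: "A negative correlation between the two would imply that higher antibody titers in the cord specimen inhibit the filial production of antibodies". A parallel but softer reading is given for cord diphtheria antibody, and a tetanus correlation is added as a control.
- **Regression.** The terms listed for it are these: "joint and separate effects of maternal antibody titers to pneumococcal polysaccharide, diphtheria and tetanus antigens, birth weight, immunization interval and other demographic variables". Study group is not named.

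For the maternal-filial objective (Secondary 2), Appendix 2 lists only a correlation coefficient. The text does not say whether the correlations are pooled across groups or run within them, or which result governs if the correlation and the group comparison disagree. Under Threats to validity, the protocol states: "Bias due to confounding factors and selection bias will be reduced by the randomization procedures".

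**The concern.** The correlation rule draws a causal conclusion from an exposure that the trial does not assign. Cord titer differs between infants partly because of the mother's vaccine and partly because mothers differ in past exposure, placental transfer and length of gestation. Some of these factors may also bear on the infant's own response. A household with more children, for example, could raise both the mother's titer and the infant's natural priming. That would push the correlation upward and could hide real inhibition. A factor acting in opposite directions on the two titers could produce a negative correlation without any inhibition.

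The protection from randomization that the protocol relies on covers the group comparison. It does not extend to a within-group correlation, covers a pooled one only in part, and does not cover the diphtheria correlation, because no maternal diphtheria vaccine is randomised. At stake is the question that motivates the trial: whether maternal antibody blunts the infant's response. As written, the plan could give two answers to it.

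**Working it through.** **1. The plan's own correlation figure.** The Sample size estimate section states 80% power for r = -0.35 with 90 subjects. By Fisher's z, power = Φ(atanh(|r|)·√(n-3) - 1.96), and atanh(0.35) = 0.3654.

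- n = 63: 0.3654 × √60 = 2.831; Φ(0.871) = 80.8%
- n = 90: 0.3654 × √87 = 3.409; Φ(1.449) = 92.6%
- n = 126: 0.3654 × √123 = 4.053; Φ(2.093) = 98.2%

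The stated 80% matches 63, the completers of one group of 90 after 30% loss. This fits a within-group analysis but does not establish that one is intended.

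**2. How much of the cord-titer variance is randomised.** With equal groups, let d be the log10 fold difference in cord GMT and s the within-group SD of log10 cord titer. The randomised share of the pooled variance is (d/2)² / [(d/2)² + s²]. The protocol gives neither d nor s, so both are assumed.

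| Cord rise | d | s = 0.4 | s = 0.5 | s = 0.6 |
|---|---|---|---|---|
| 2-fold | 0.301 | 12% | 8% | 6% |
| 3-fold | 0.477 | 26% | 19% | 14% |
| 4-fold | 0.602 | 36% | 27% | 20% |
| 10-fold | 1.000 | 61% | 50% | 41% |

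The share passes one half when d exceeds 2s: above 6.3-fold at s = 0.4, 10-fold at 0.5 and 15.8-fold at 0.6. Within one group d = 0, so the share is 0%. It is also 0% for cord diphtheria antibody, since mothers receive only the study vaccine and tetanus toxoid.

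**3. Whether the two rules can disagree.** Simulation with 63 per group, final SD 0.606 (Table 1, 19F), cord rise 2- or 3-fold, s = 0.4 or 0.5, 4,000 trials per setting, two-sided 5% tests:

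- No effect of maternal vaccination, but a non-causal within-group r of -0.35: the pooled correlation is significantly negative in 93-97% of trials; the group t-test shows a lower titer in about 2%.
- Vaccination truly halves the final GMT, but confounding makes the within-group r weakly positive (0.13 to 0.17): the t-test shows inhibition in 78-79%; the pooled correlation in 0-4%.

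These settings show that disagreement is possible. They do not say how likely it is.

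**4. What the group contrast can and cannot detect.** Suppose the true slope of log10 final titer on log10 cord titer is b = -0.30. The standard error of the group difference is 0.606 × √(2/63) = 0.108.

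- d = 0.30: difference 0.30 × 0.30 = 0.09; power 13%
- d = 0.60: difference 0.30 × 0.60 = 0.18; power 38%

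For the pooled correlation with s = 0.5 and n = 126, add a shared-exposure correlation k within groups. The pooled covariance is b·s² + k·s·0.606 + 0.25·b·d², and the variances are s² + d²/4 for cord titer and 0.606² + (b·d)²/4 for final titer. Over d = 0.30 to 0.60, the chance of a significant negative r is:

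| k | Chance |
|---|---|
| 0 | 83-90% |
| +0.1 | 44-62% |
| +0.2 | 11-25% |
| +0.3 | 1-5% |

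So the correlation is the more sensitive tool when there is no confounding and loses that advantage quickly when there is. The group contrast is unconfounded but weak against a modest slope.

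**The case against.** The best defence is that the plan already ranks the analyses. The randomised GMT comparison belongs to the primary objective, and the correlation serves secondary ones. The tetanus correlation is a partial control, household counts are recorded at baseline, and the regression admits demographic variables and birth weight. Pooling and a full covariate list are often left to an analysis plan, and nothing forbids a group term. All of this stands as mitigation. It does not remove the printed causal reading, which attaches to the unadjusted correlation, and covariate adjustment does not turn cord titer into a randomised exposure. Tetanus antibody also cannot reveal confounding specific to pneumococcal exposure.

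A second objection also stands: the group contrast cannot replace the correlation. It has only 13-38% power against the modest slope above, and no randomised contrast exists for diphtheria antibody.

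A reader might infer three stronger points that the documents do not support.

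- *That any inhibition finding would rest mostly on non-randomised differences.* For a pooled correlation this depends on the assumed cord rise; at 10-fold the randomised share is 50-61% for SD 0.4-0.5.
- *That immunization interval has meaning only in the pneumococcal group.* Every mother is injected and receives tetanus toxoid at the same visit, and the regression also models tetanus titers.
- *That priming is a demonstrated bias.* The Background says only: "This may also induce the effect of priming in the newborn". If it added 0.2 log10 in group 2 (assumed, with a within-group r of -0.35), a slope fitted without a group term would keep 77-89% of its value and its sign. This is an illustration only.

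**Conclusion.** The point holds for the secondary maternal-filial analyses. The protocol attaches a causal reading to a correlation whose exposure is not randomised, leaves pooling open and does not name study group in the regression. For a within-group correlation and for cord diphtheria antibody, the evidence is wholly observational. For a pooled polysaccharide correlation, the randomised share is about 6-36% under an assumed 2- to 4-fold rise and SD 0.4-0.6, and 50-61% at 10-fold and SD 0.4-0.5. These shares, and the simulated disagreements, rest on inputs that the protocol does not give.

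The primary analysis is not affected. The randomised group 1 versus 2 comparison is sound as a contrast and should carry the causal conclusion about maternal immunization. The correlation remains useful as supporting evidence, provided that it is labelled as association. It would go too far to say that inhibition may be concluded or excluded from the group contrast alone.

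**What to change.** In Data analysis and in Appendix 2 (Secondary 2):

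1. Add study group to the regression. For each serotype, fit log10 18-week titer on study group and on log10 cord titer centred on its group mean. Report the randomised group contrast and the within-group slope separately. Because of the centring, the group term in this two-term model is the plain difference between group means.
2. Reword the inference sentence: a negative slope is an association consistent with inhibition but open to confounding. Use the same wording for the diphtheria correlation, and note that no randomised contrast exists there.
3. State that the causal conclusion about maternal immunization comes from the randomised GMT comparison, and that a non-significant group contrast does not exclude a modest inhibitory slope.
4. Optionally, repeat the model with the infant's 6-week pre-dose titer, which the project summary names alongside the birth titer as a measure of passive antibody but which the correlation in Data analysis does not use.

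The cost is a few sentences and model terms, and a within-group slope somewhat less precise than a pooled one. No new specimens, visits or subjects are needed.
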